## 6. GENERAL CONSIDERATIONS

Besides data listings, all measures will be summarized by randomized arm and/or overall. Continuous variables will be summarized using descriptive statistics such as number of observations (n), mean, standard deviation, minimum, and maximum. Categorical variables will be tabulated using frequency (n), sometimes along with percentage (%).

All data manipulations and descriptive summaries will be implemented using SAS®, Version 9.4 or later.

### 6.1. Adjustments for Covariates

Covariate adjustments are not applicable to this study.

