16.2.2. Statistical Hypotheses and Level of Significance

No statistical hypothesis is defined for this study.

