16.2.3. Randomization

The first 6 subjects will be randomized to Arm 1 and Arm 2 in a 1:1 ratio in Stage 1. If the safety and tolerability at Week 4 are acceptable, remaining approximately 70 subjects will be randomized to all Arms in a 1:2:2 ratio in Stage 2. To balance the randomization, subjects will be stratified by subgroups on the central reading center's assessment of lesion type, up to approximately one third (1/3) of the subjects in each arm should have PCV in Stage 2.

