**Figure 1: Study Design Diagram**

### 3.2. Randomization and Masking

In Stage 1, the first 6 subjects will be randomized to either Arm 1 or Arm 2 in a 1:1 ratio. A blocked randomization with a fixed block size of 2 will be employed.

In Stage 2, approximately 70 subjects will be randomized to all three Arms in a 1:2:2 ratios. A blocked randomization with a fixed block size of 5 stratified by lesion type (polypoidal choroidal vasculopathy [PCV] vs. non-PCV) will be employed. Approximately one third (1/3) of the subjects in each arm are expected to have PCV in Stage 2.

This is a double-masked study, where the subjects and the examiners including the Principal Investigator (PI), are masked to the treatment regimen. However, the designated injecting physician (who is not the PI) will not be masked to the treatment regimen.

The Sponsor will have masked and unmasked data review teams. The designated Safety Review Team will review the safety data of the 6 subjects in Stage 1 to determine if the safety and tolerability of the doses at Week 4 are acceptable. In case of a medical emergency, the Principal

Investigator or site staff may reveal the treatment information by unmasking in the Interactive Web Response Systems (IWRS).

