### 4.2.3. Change and Percent Change from Baseline

The change and the percent change from baseline in a measure at a post-baseline visit will be defined as:

- Change = score at the post-baseline visit – baseline score.
- Percent change from baseline =  $100 \times \text{change} / (\text{baseline score})$ .

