### **8.1. Primary Endpoint**

#### **8.1.1. Primary Analysis**

The primary efficacy endpoint is mean change from baseline in BCVA at Week 24. No formal statistical hypothesis testing will be implemented for the primary endpoint. Descriptive summaries will be provided by each planned treatment arm. The differences in mean change between Arm 2 or 3 and Arm 1, as well as the corresponding 95% confidence intervals based on t-test without multiplicity adjustment will also be provided. Descriptive summaries of BCVA measured at Week 28 and Week 32 will be provided, in which any records after the rescue injection(s) will be censored.

The primary analyses will be performed on the FAS. Besides the summary tables, plots of BCVA measures versus analysis visit will be provided. BCVA score, and percent change from baseline will also be summarized.

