### **8.2. Analyses of Secondary Endpoints**

#### **8.2.1. Primary Analysis**

Frequency and percentage of subjects with BCVA improvement of  $\geq 15$  ETDRS letters (3-line gainers); within 15 letters change (stable) and loss of  $\geq 15$  letters from baseline at Week 24 will be provided based on FAS. The differences in proportion between Arm 2 or 3 and Arm 1, as well as the corresponding 95% confidence intervals based on t-test without multiplicity adjustment will be provided. Besides the summary table, bar plot will be performed.

Change from baseline in CST, MV, CRLT, total lesion area, total area of CNV, and GLD of the total lesion area at Week 24 will be summarized descriptively by treatment arms based on observed data. The differences in mean change between Arm 2 or 3 and Arm 1, and the corresponding 95% confidence intervals based on t-test without multiplicity adjustment will be provided. Scores and percent change from baseline will be provided. Plots of measurement and

change from baseline versus analysis visit will also be provided. Frequency and percentage of subjects with ‘ungradable’ data will be provided.

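### The SAP reports between-arm differences in change with t-based intervals but plans no estimate adjusted for baseline and lesion type; a supportive ANCOVA would be a cheap addition

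*SAP*

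**What the plan says.** SAP 6.1 consists of one sentence: "Covariate adjustments are not applicable to this study". No reason is given.

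The SAP does more than describe each arm separately. For the primary endpoint, section 8.1.1 adds "The differences in mean change between Arm 2 or 3 and Arm 1, as well as the corresponding 95% confidence intervals based on t-test". For CST, macular volume, CRLT, total lesion area, CNV area and greatest linear dimension, section 8.2.1 adds "The differences in mean change between Arm 2 or 3 and Arm 1, and the corresponding 95% confidence intervals based on t-test".

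Section 4.2.3 defines the quantity compared: "Change = score at the post-baseline visit – baseline score". Section 3.2 describes the Stage 2 allocation as "A blocked randomization with a fixed block size of 5 stratified by lesion type", that is, PCV against non-PCV. Protocol 16.2.3 adds that "up to approximately one third (1/3) of the subjects in each arm should have PCV in Stage 2".

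Lesion type appears again as a baseline characteristic (SAP 7.2) and as a subgroup for the primary endpoint (SAP 8.3). The sensitivity analyses in 8.1.2 and 8.2.2 cover the per-protocol set, LOCF (BCVA only) and censoring after a skipped injection. None of them gives an adjusted difference.

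On inference, Protocol 16.2.2 says "No statistical hypothesis is defined for this study".

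**The concern.** Once differences between arms are reported with confidence intervals, covariate adjustment is a real choice. The planned intervals fix the coefficient of baseline at 1, whatever the data show, and ignore the one factor judged important enough to stratify on.

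Two things are at stake, both modest. The interval may be wider than it needs to be. And with only 17 control subjects, a chance difference in baseline BCVA between arms passes in part into the difference in change, with no adjusted estimate beside it for the reader to compare. No error rate is involved, because nothing is tested.

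**Working it through.** **Arm sizes.** Stage 1 gives 3 + 3 + 0. Stage 2 gives 70 subjects at 1:2:2, or 14 + 28 + 28. The sum is 17 + 31 + 28 = 76, which reproduces SAP 3.3.

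**Assumed inputs.** The documents give no SD, correlation or PCV effect.
- Baseline BCVA SD s = 10 letters. Protocol 8.1 restricts entry to 25 to 65 letters; a uniform spread over that range would give 40/√12 = 11.5.
- rho, the baseline to Week 24 correlation: 0.5 to 0.9.
- r, the Week 24 SD divided by the baseline SD: 1.0 to 1.4.
- Lesion type is first taken as uninformative.

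**Formulas, Arm 3 minus Arm 1**, with k = √(1/17 + 1/28) = 0.3075:
- SD of change = s√(1 + r² − 2·rho·r). Unadjusted half-width = t(0.975, 73) × SD of change × k, with error pooled over three arms and t = 1.993.
- ANCOVA residual SD = s·r·√(1 − rho²). Adjusted half-width = t(0.975, 71) × residual SD × k × √(1 + 2/70), with t = 1.994. The last factor is the average price of estimating two covariates.

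| r | rho | SD of change | Residual SD | Unadjusted | ANCOVA | Change in width |
|---|---|---|---|---|---|---|
| 1.0 | 0.5 | 10.00 | 8.66 | 6.13 | 5.38 | −12.1% |
| 1.0 | 0.7 | 7.75 | 7.14 | 4.75 | 4.44 | −6.5% |
| 1.0 | 0.8 | 6.32 | 6.00 | 3.88 | 3.73 | −3.7% |
| 1.0 | 0.9 | 4.47 | 4.36 | 2.74 | 2.71 | −1.1% |
| 1.2 | 0.5 | 11.14 | 10.39 | 6.82 | 6.46 | −5.3% |
| 1.2 | 0.7 | 8.72 | 8.57 | 5.34 | 5.33 | −0.3% |
| 1.2 | 0.8 | 7.21 | 7.20 | 4.42 | 4.48 | +1.3% |
| 1.2 | 0.9 | 5.29 | 5.23 | 3.24 | 3.25 | +0.3% |
| 1.4 | 0.5 | 12.49 | 12.12 | 7.65 | 7.54 | −1.5% |
| 1.4 | 0.7 | 10.00 | 10.00 | 6.13 | 6.22 | +1.4% |
| 1.4 | 0.8 | 8.49 | 8.40 | 5.20 | 5.22 | +0.4% |
| 1.4 | 0.9 | 6.63 | 6.10 | 4.06 | 3.79 | −6.7% |

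The percentages do not depend on s. At rho 0.7 and r = 1, s = 8 gives 3.80 against 3.55 and s = 11.5 gives 5.46 against 5.11. They are the same for Arm 2 minus Arm 1 (for example 6.01 against 5.29 at rho 0.5, r = 1).

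**Simulation with the entry limits.** With baseline truncated to 25 to 65 letters, r = 1 and no PCV effect (2000 runs per setting), the gains at rho 0.5, 0.7, 0.8 and 0.9 are 10%, 5%, 3% and 1%.

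**Lesion type.** With a PCV share p, a PCV effect of d letters and the residual SD of 7.14 from rho 0.7, r = 1, the further narrowing is 1 − 1/√(1 + p(1 − p)d²/7.14²). At p = 1/3, d = 2, 4 and 6 give 0.9%, 3.3% and 7.0%. The Protocol words one third as an upper limit; at p = 0.2 the figures are 0.6%, 2.4% and 5.2%. This concerns the reported width, since stratification already balances the estimate itself.

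**Chance imbalance.** The Arm 3 minus Arm 1 baseline difference has SD 10 × 0.3075 = 3.1 letters. A one-SD imbalance shifts the unadjusted difference by (rho·r − 1) × 3.07. For rho 0.5, 0.7, 0.8 and 0.9 this is −1.5, −0.9, −0.6 and −0.3 at r = 1, and −1.2, −0.5, −0.1 and +0.2 at r = 1.2.

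**Validity of the planned interval.** In a separate simulation of Arm 2 against Arm 1 (6000 runs per case), the unadjusted interval covered 94.7% to 96.0%. It was slightly conservative (96.0%) in the case with rho 0.7, r = 1 and a PCV effect of half an SD of change.

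**The case against.** The plan is coherent as written. The study is exploratory, no hypothesis is defined, the sample size has no statistical basis, and Protocol 16.6.1 asks for descriptive statistics. Under randomization the unadjusted difference is unbiased and its interval valid. All of this stands, and it limits the weight of the point.

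The benefit rests wholly on assumed values. The equal-spread rows may also be favourable: entry criteria restrict baseline BCVA but nothing restricts Week 24, so a ratio above 1 is plausible. At 1.2 the change runs only from 5% narrower to 1% wider. This stands too, and is why a range is given and no single percentage.

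Chance imbalance is already allowed for in the width of the unadjusted interval, and baseline BCVA and lesion type will be tabulated by arm. That is correct, but a table lets the reader see an imbalance without saying how far it moved the difference; an adjusted estimate does.

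The SAP does not say that the t-interval pools error over three arms. A two-sample interval for Arm 3 against Arm 1 (43 df) has half-width 6.20 instead of 6.13 at an SD of change of 10. The comparison above is therefore slightly unfavourable to ANCOVA.

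A reader might infer that leaving out the stratification factor makes the planned intervals wrong. The documents and the coverage check do not support that: omitting a balanced prognostic factor makes the interval a little wide, not too narrow.

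**Conclusion.** The point holds as a suggested improvement of low weight. The planned differences use baseline only by subtraction and never use lesion type, and no other planned analysis supplies an adjusted difference.

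For BCVA, under the assumed ranges and with lesion type uninformative, adjustment changes the Arm 3 minus Arm 1 interval by between about 12% narrower (about 10% under the entry limits) and about 1% wider. A prognostic lesion type would add roughly 1% to 7% at one third PCV. The correction for a one-SD chance baseline imbalance is at most about 1.5 letters.

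Two simpler conclusions are tempting and unsupported. One is that adjustment is sure to sharpen this trial's estimates; several rows of the table show no gain or a slight loss. The other is that baseline adds nothing once the correlation is high or Week 24 spread exceeds baseline spread; the table shows 5% at r = 1.2, rho 0.5 and 7% at r = 1.4, rho 0.9. The gain follows no simple rule in either quantity. For the OCT and FA endpoints it is not quantified.

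**What to change.** Before unmasking, amend SAP 6.1, 8.1.1 and the continuous endpoints of 8.2.1. Suggested text:

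> As a supportive analysis, Week 24 change in BCVA, CST, MV, CRLT, total lesion area, CNV area and GLD will each be analysed by ANCOVA with arm (three levels), the baseline value of that measure and lesion type (PCV or non-PCV). Adjusted differences from Arm 1 with 95% confidence intervals will be shown beside the planned summaries and unadjusted t-intervals.

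The planned summaries and t-intervals stay as they are, and BCVA is the main case.

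The cost is a few lines of text and one model form. Baseline values and lesion type are already summarised under SAP 7.2, and Protocol 7.5.2.1 has the reading center confirm lesion type before randomization. The statistical price is two degrees of freedom: if both covariates are uninformative, the interval widens by (1.994/1.993) × √(1 + 2/70) − 1, or about 1.5%. The added differences would carry no multiplicity adjustment, as with the planned ones, and should be labelled supportive.

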### 6.2. Handling of Missing Data

For safety measures, missing scores will not be imputed for data summaries.

For efficacy measures, the last-observation-carried-forward (LOCF) approach may be used to impute missing post-baseline values in sensitivity analysis. Baseline scores will not be carried forward.

Completely or partially missing onset and resolution dates of medical events, i.e., medical history events and AEs will be imputed in a conservative fashion as follows.

Date	Type of Missing Date	Handling of Missing Date
Event onset date (e.g., YYYY-MM-DD)	Completely missing	No imputation will be applied.
	Only YYYY is available	Use the first day of YYYY to impute the missing month and day of the onset date
	YYYY and MM are available but DD is missing	Use the first day of MM to impute the missing day of the onset date
Event resolution date (e.g., YYYY-MM-DD)	Completely missing	No imputation will be applied
	Only YYYY is available	Use the last day of YYYY to impute the missing month and day of the resolution date
	YYYY and MM are available but DD is missing	Use the last day of MM to impute the missing day of the resolution date

Same rules will be followed to impute completely or partially missing start and end dates of non-study medications.

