16.4. Handling of Missing Values

Primary analysis of the primary efficacy endpoint will be based on the observed cases. Missing BCVA measurements will be imputed using the Last-Observation-Carried-Forward (LOCF) approach as a sensitivity analysis. For safety measures, missing scores will not be imputed for data summaries.

Completely or partially missing onset and resolution dates for AEs and completely or partially missing start and end dates of concomitant medications will be imputed in a conservative fashion that will be detailed in the SAP.

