### 4.3. Safety-Related Definitions

#### 4.3.1. Adverse Event

An AE is any untoward medical occurrence in a subject administered a pharmaceutical product and which does not necessarily have a causal relationship with the study drug(s).

An on-study AE can occur at any time after the date of informed consent through the last study visit. An AE will be considered as treatment-emergent if the AE onset occurs on or after the analysis period start date and prior to or on the on-treatment analysis period end date as defined in [Section 4.1.4](#). Treatment-emergent AEs are a subset of on-study AEs. Both on-study and treatment-emergent AEs are to be recorded, but only treatment-emergent AEs will be tabulated.

Each AE will be classified into a system organ class (SOC) and coded to a preferred term (PT) using Medical Dictionary for Regulatory Activities (MedDRA), version 20.0 published in 2017.

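### SAP 6.2 leaves a completely missing AE onset date unimputed, against Protocol 16.4 and its own lead-in, so such an AE is unclassified and not tabulated

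*SAP*

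**What the plan says.** Protocol 16.4 (Handling of Missing Values) states: "Completely or partially missing onset and resolution dates for AEs and completely or partially missing start and end dates of concomitant medications will be imputed". The method is to be "imputed in a conservative fashion that will be detailed in the SAP".

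The lead-in to the table in SAP 6.2 (Handling of Missing Data) makes the same commitment: "Completely or partially missing onset and resolution dates of medical events, i.e., medical history events and AEs will be imputed in a conservative fashion". The table gives three rules for an onset date:

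- Completely missing: "No imputation will be applied".
- Year known: "Use the first day of YYYY to impute the missing month and day of the onset date".
- Year and month known: "Use the first day of MM to impute the missing day of the onset date".

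SAP 6.2 then extends these rules to the start and end dates of non-study medications.

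SAP 4.3.1 (Adverse Event) sets the condition for counting: "An AE will be considered as treatment-emergent if the AE onset occurs on or after the analysis period start date", with an upper bound at the end of the on-treatment period. Both on-study and treatment-emergent AEs are recorded, "but only treatment-emergent AEs will be tabulated".

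SAP Table 2 starts the on-treatment period, and the entire-study period for safety, at the first Lucentis injection. SAP 9.1 asks for AE tables for the on-treatment, follow-up and entire-study periods. It also asks for listings of AEs, SAEs and ESIs, and does not limit these to treatment-emergent events.

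**The concern.** For a safety rule, a conservative treatment of an unknown date is one that counts the event. The row for a completely missing onset does not do that. It supplies no date, and the sections that decide what is tabulated all work from the date. Nothing in the SAP says how an AE without an onset date is to be classified.

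The overall, ocular, related, serious and special-interest AE tables are at stake. Safety is part of the primary objective, the safety results are descriptive, and the arms have 17, 31 and 28 subjects, so a single subject can visibly move a rate.

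The two rows for partial onset dates can have the same effect. Neither has a floor at the first injection, so an AE in the month or year of first dosing can be moved to before treatment.

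**Working it through.** The plan states no figure on this point, so there is none to reproduce. The check applies SAP 6.2, SAP 4.3.1 and SAP Table 2 literally to test events.

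**Step 1. Texts side by side.**

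| Place | Completely missing AE onset |
|---|---|
| Protocol 16.4 | Imputed, conservatively; detail left to the SAP |
| SAP 6.2, lead-in | Imputed, conservatively |
| SAP 6.2, table | Not imputed |
| SAP 4.3.1, Table 2, 9.1 | No default for an unknown onset |

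The table contradicts the protocol and its own lead-in.

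**Step 2. Classification.** Assume, for illustration, a first injection on 15 May 2018. Week 24 (Day 169) is 168 days later, 30 October 2018. Exit (Day 225) is 224 days later, 25 December 2018. An event enters a table only if its date after SAP 6.2 can be placed inside the period.

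| Recorded onset | Date after SAP 6.2 | On-treatment | Follow-up | Entire study |
|---|---|---|---|---|
| Nothing | None | no | no | no |
| 2018 | 1 Jan 2018 | no | no | no |
| May 2018 | 1 May 2018 | no | no | no |
| July 2018 | 1 July 2018 | yes | no | yes |
| Nothing, but onset set to first injection | 15 May 2018 | yes | no | yes |

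The undated AE cannot be placed in any period.

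**Step 3. Reach of the partial-date rows.** Assume first injections fall evenly over a 365-day year. A month-only onset in the dosing month is moved before dosing unless dosing was on the first of a month: (365 − 12)/365 = 353/365 = 96.7%. A year-only onset in the dosing year is moved before dosing unless dosing was on 1 January: 364/365 = 99.7%.

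**Step 4. Weight of one lost subject.** SAP 9.1 counts subjects, so the rate changes by 1/n if the undated AE is that subject's only event in the category. Arm sizes are from SAP 3.3; I assume all subjects are treated as randomised.

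- Arm 1: 1/17 = 5.9 points
- Arm 2: 1/31 = 3.2 points
- Arm 3: 1/28 = 3.6 points
- Overall: 1/76 = 1.3 points

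**Step 5. Which default errs less.** AEs are recorded from consent. Screening covers at most Day −14 to Day −1 (14 days), the on-treatment period Days 1 to 169 (169 days) and follow-up Days 170 to 225 (56 days): 14 + 169 + 56 = 239 days. If onset were equally likely on any day (an assumption), 14/239 = 5.9% of undated AEs would be pre-treatment, 169/239 = 70.7% on-treatment and 56/239 = 23.4% in follow-up. Leaving all of them untabulated would be wrong for about 94%.

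**The case against.** The strongest reply is that leaving a date blank does not classify the event. A programmer could leave the onset missing, call the AE treatment-emergent and comply with SAP 6.2. That stands against the stronger reading that a reader might infer, namely that under the SAP such an AE can never be treatment-emergent. SAP 4.3.1 is silent on unknown onset, so the exact statement is that the event is left unclassified. An argument from how SAS sorts missing dates adds nothing, since the documents specify no such programming.

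The sentence in SAP 4.3.1 that limits tabulation to treatment-emergent AEs cannot be an absolute filter either, because SAP 9.1 also asks for follow-up tables, which lie beyond the on-treatment end date. This does not rescue the undated AE: Table 2 bounds the follow-up and entire-study periods by dates as well.

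The protocol does delegate the detail to the SAP. But it delegates the detail of a conservative imputation, and supplying none does not carry that out.

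In practice the case should be rare. AEs are queried at every visit from Day 1, start and end dates are recorded, and the data undergo source verification and edit checks. A wholly unknown onset is least plausible for serious and special-interest events, which must be reported within 24 hours. This stands, and it limits the size of the problem. The protocol nevertheless foresaw the case and required a rule.

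For medications, a reader might infer that a drug with neither date is neither prior nor concomitant. The documents do not establish this. Protocol 9.2 records a stop date only if applicable, so a blank one can mean the drug is ongoing, and an ongoing drug overlaps treatment under SAP 4.4.1. The classification needs stating, but no loss has been shown.

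**Conclusion.** The point holds as a conflict of wording with a non-conservative result when the plan is followed literally. A completely missing AE onset stays unimputed, contrary to Protocol 16.4 and the SAP's own lead-in, and with no default for unknown onset the event is not tabulated. It remains in the listings, so the documents do not support a claim that it disappears from the report.

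The size is at most 5.9, 3.2 or 3.6 points per lost subject in Arms 1, 2 and 3. That bound assumes the undated AE is the subject's only event in the category; a subject with another dated event there leaves the rate unchanged. A reader might go on to expect a shift of several points in the actual results. The documents give no frequency of missing onset dates, so they support only the per-subject bound.

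The correction must include partial dates, probably the commoner route to the same loss. If only the undated row were repaired, an AE with no date would be treatment-emergent while one known to have begun in the dosing year usually would not.

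**What to change.** Amend SAP 6.2, for AEs only, so that medical history events keep their present rows:

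- **Completely missing onset.** Treat the AE as treatment-emergent, for example by setting onset to the date of the first Lucentis injection, unless a known resolution date precedes that injection.
- **Partial onset.** Where the known month or year is compatible with that of the first injection, use the later of the imputed date and the first injection date, unless a known resolution date is earlier.
- **Medications.** State that a medication with both dates missing is counted as concomitant.
- **Listings.** Flag every imputed date.
- **Lead-in.** Reword it to agree with the table.

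The cost is a few lines of SAP text and the matching programming. An occasional pre-treatment event may be counted as treatment-emergent. If onset is set to the first injection, some follow-up events would also be shown as on-treatment. Both errors count an event that the present rule leaves out, which is the conservative direction the protocol asks for, and the flags let a reader see them.

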12.1.1.2. Reporting Adverse Events

AEs, whether spontaneously reported by the subject or noted by authorized study personnel, will be recorded in the subject's medical record and on the appropriate AE eCRF. Each recorded AE will be described by its duration (i.e., start and end dates), frequency, severity, regulatory seriousness criteria if applicable, suspected relationship to the study drug(s), relation to injection procedure, location, actions taken and outcome.

AEs that occur after any subject has provided written informed consent, before treatment, during treatment, or until study exit visit, whether or not they are related to the study, must be recorded. To improve the quality and precision of acquired AE data, Clinical Investigators should observe the following guidelines:

- Whenever possible, use recognized medical terms when recording. Do not use colloquialisms and/or abbreviations.
- If known, record the diagnosis (i.e., disease or syndrome) rather than component signs and symptoms and /or laboratory or test findings (e.g., record congestive heart failure rather than dyspnea, rales, and cyanosis, and enlarged heart on chest x-ray). However, other events that are considered unrelated to an encountered syndrome or disease should be recorded as individual AEs (e.g., if congestive heart failure and severe headache are observed at the same time and are clinically unrelated, each event should be recorded as an individual AE).

If the diagnosis is not known, then record the leading component sign, symptom or test finding and describe the other clinically related findings in the narrative description of the case. A suspected diagnosis can be used and described as such

(e.g., record suspected or probable myocardial infarction); this has to be updated in the clinical database once the diagnosis is confirmed.

AEs occurring secondary to other events (e.g., sequelae) should be identified by the primary cause. A primary AE, if clearly identifiable, generally represents the most accurate clinical term. If a primary AE is recorded, events occurring secondary to the primary event should be described in the narrative description of the case. For example:

The subject developed orthostatic hypotension and subsequently fainted and fell to the floor wherein she experienced a head trauma and neck pain.

The primary AE in this example is orthostatic hypotension. The fall, head trauma and neck pain should be described in the narrative description of the case.

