**Table 2: Analysis Periods**

Analysis Period	Analysis Period Start Date	Analysis Period End Date
On-treatment Period	The date of the first Lucentis® injection	The date of the Week 24 visit, or the Study Exit date, whichever came first
Follow-up Period	The date of the first day after Week 24 visit	The Study Exit date
Entire Study	Efficacy: the date of randomization; Safety: the date of the first Lucentis® injection	The Study Exit date

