### **9.1. Adverse Event**

Subjects with any AE(s), SAE(s), SAR(s), serious SAR(s) and ESI(s) will be tabulated for each actual treatment received. Besides the overall AE summary, subjects with any AE(s) will be tabulated by SOC and PT specified in MedDRA Version 20.0. Subjects with any AE(s) will also be tabulated by SOC, PT and maximum severity. A subject who experienced multiple AEs within a SOC or PT will be counted only once at the maximum severity for that SOC or PT. SAEs, SARs, and Serious SARs will be tabulated similarly.

Summaries for ocular AEs and non-ocular AEs will also be performed. Ocular AEs, ocular SAEs and ocular SARs will be summarized for study eyes and fellow eyes separately. Any ocular AE that occurred simultaneously to both eyes will be counted once for both the study eye and the fellow eye.

All AE tabulations will be performed on the Safety population for the On-treatment period, Follow-up period and entire study.

AEs, AEs leading to death, AEs leading to discontinuation, SAEs, and ESIs, if any, will be listed separately.

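### SAP 6.2 does not floor partial AE onset dates at the first injection, so some post-injection AEs are dated before treatment and drop out of the AE tables

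*SAP*

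**What the plan says.** SAP 6.2 states that incomplete dates of medical history events and AEs "will be imputed in a conservative fashion as follows"; Protocol 16.4 also promises a conservative approach and leaves the detail to the SAP. The SAP's onset rules are:

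- Day missing: "Use the first day of MM to impute the missing day of the onset date".
- Month and day missing: "Use the first day of YYYY to impute the missing month and day of the onset date".
- Date completely missing: no imputation.

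Three other places decide what happens to the imputed date:

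- SAP 4.3.1: "An AE will be considered as treatment-emergent if the AE onset occurs on or after the analysis period start date", and "only treatment-emergent AEs will be tabulated".
- SAP Table 2: the On-treatment Period starts at the first Lucentis injection. The Entire Study period has the same start for safety: "Safety: the date of the first Lucentis® injection". The Follow-up Period starts after Week 24.
- SAP 9.1: AE tables are produced for those three periods. Listings are also produced: "AEs, AEs leading to death, AEs leading to discontinuation, SAEs, and ESIs, if any, will be listed separately".

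Neither document adds a floor at the first injection, lets the resolution date inform the onset, or presumes treatment emergence when the date is ambiguous.

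**The concern.** Taking the earliest possible onset suits medical history, which shares the table in 6.2. For an AE in the month or year of the first injection it does the opposite of what a safety analysis needs: an event that may be, or certainly is, post-injection is given a pre-treatment date and left out of the tabulated rates. Safety is half of the primary objective and the arms are small (17, 31 and 28). One subject lost from an AE row moves that arm's rate by 1/17 = 5.9, 1/31 = 3.2 or 1/28 = 3.6 percentage points.

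A related gap is that an AE with a completely missing onset gets no date, and neither document says whether it counts as treatment-emergent. Programmers would have to decide that for themselves.

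**Working it through.** The documents give no figure on this point, so there is nothing to reproduce. The check applies the written rules to dates.

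**Worked cases** (first injection 15 March 2018 unless stated)

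| True onset | Recorded as | Imputed onset | Tabulated under 6.2? | With a floor |
|---|---|---|---|---|
| 20 Mar 2018 | Mar 2018 | 1 Mar 2018 | No | 15 Mar 2018, yes |
| 20 Mar 2018 | 2018 | 1 Jan 2018 | No | 15 Mar 2018, yes |
| 20 Aug 2018 | 2018 | 1 Jan 2018 | No | 15 Mar 2018, yes |
| 3 Apr 2018 | Apr 2018 | 1 Apr 2018 | Yes | unchanged |
| 20 Mar 2018, first injection 1 Mar 2018 | Mar 2018 | 1 Mar 2018 | Yes | unchanged |

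The last row is the exception: no day-missing event is lost if the first injection was on the 1st of the month. For year-only dates the exception is 1 January.

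**Share of partially dated events affected**

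Inputs and assumptions:

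- The first subject is expected in July 2017 (Protocol synopsis). First injections are assumed uniform from 1 July 2017.
- Last completion is expected in January 2020 (synopsis). Week 32 is Day 225, so the latest first injection is 31 January 2020 − 224 days = 21 June 2019. End dates from 31 December 2018 to 30 June 2019 were tried.
- True onset is assumed uniform over Days 1–169, where Day 169 is the Week 24 target.
- An event is lost if its imputed onset is before Day 1.

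*Day missing, by hand.* If the first injection is on day k of a month of L days (k ≥ 2), onsets on the remaining L − k + 1 days of that month are lost. Averaged over k, this is (L − 1)/2 days. With L = 365/12 = 30.4, that is 14.7 days, and 14.7/169 = 8.7%.

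*Enumeration of every injection date and onset day.*

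| Last first injection | Pairs | Day-missing lost | Year-only lost |
|---|---|---|---|
| 31 Dec 2018 | 549 × 169 = 92,781 | 8.7% | 69.2% |
| 21 Jun 2019 | 721 × 169 = 121,849 | 8.8% | 76.4% |
| 30 Jun 2019 | 730 × 169 = 123,370 | 8.7% | 76.7% |

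With the 21 June 2019 end date, 93.6% of day-missing events whose true onset is in the injection month are lost, and 99.6% of year-only events whose true onset is in the injection year. With a floor at the first injection, none are lost.

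**The Week 24 boundary.** For true onsets on Days 170–225, about 26% of day-missing events move back into On-treatment and none are dated before Day 1. Of year-only events, 46–61% move into On-treatment and 31–46% are dated before Day 1. These follow-up figures assume that Follow-up AEs are tabulated, as SAP 9.1 says. SAP 4.3.1 ends treatment emergence with the On-treatment Period and, read literally, would leave those events out of the tables anyway.

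**Number of events.** The documents do not say how many partial dates to expect. Purely as an illustration, assume 100–400 AEs with 1–10% missing the day: 100 × 0.01 × 0.087 = 0.09 and 400 × 0.10 × 0.087 = 3.5 AEs lost.

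**The case against.** The mechanism is not in dispute; its size is. The best counter-arguments are these.

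- **The exposed window is well observed.** In the enumeration every lost day-missing onset falls on Days 1–30, and about 51% fall on Days 1–9. AEs are assessed after each Day 1 injection, at Week 1 and at Week 4, and also on Day 3 for subjects who consented before Version 4.0. Partial dates should be rarer there than the uniform assumption implies, so 8.7% is probably high. This stands.
- **Year-only dates should be very rare.** Scheduled gaps are about four weeks or less, and start dates are recorded and monitored. The 69–77% is the consequence when such a date occurs, not an expected loss. This stands.
- **Tables count subjects, not events.** SAP 9.1 counts a subject once per system organ class or preferred term, so a lost AE changes a cell only if that subject has no other tabulated event there. This stands and reduces the effect further.
- **Consequences are limited.** The study is descriptive, the rule is the same in every arm, and the events remain listed, with SAEs and ESIs listed separately. This is fair, but a listing does not correct a tabulated rate.
- **Conservative is undefined.** Earliest onset with latest resolution is conservative for duration, and at Week 24 the rule over-includes. That is true, but it does not make the rule conservative for treatment emergence at the first injection, which decides whether an AE is tabulated at all.

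**Conclusion.** The concern holds. Followed as written, SAP 6.2, 4.3.1 and Table 2 together place a post-injection AE with a partial date in the month or year of first injection outside every AE table, apart from the first-of-month and 1 January exceptions. At that boundary the rule contradicts the stated conservative aim.

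The 8.7% and 69–77% shares rest on the uniform assumptions above and apply only to partially dated AEs. The absolute effect is probably small and cannot be computed from the documents. It should be corrected because the error has a known direction and the correction is cheap; it does not threaten the study's conclusions by itself.

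**What to change.** Add to the SAP 6.2 table, for AEs only:

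1. If the known month and year of onset, or the known year alone, equals that of the first Lucentis injection, impute the later of the first-day date and the first Lucentis injection date.
2. Do not apply this if the resolution date as recorded, not as imputed, shows that the AE ended before that injection. A partial resolution date counts only if its known part settles the matter.
3. Otherwise keep the first-day rule.
4. For a completely missing onset, impute no date, but classify the AE as treatment-emergent unless the recorded resolution date precedes the first injection.

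Leave the rules for medical history and medications unchanged.

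The cost is a few lines of text and a small programming change. There are two downsides. The protocol records "AEs that occur after any subject has provided written informed consent, before treatment, during treatment, or until study exit visit", so a few poorly dated pre-treatment AEs may be counted as treatment-emergent; that error is in the conservative direction. The floor also leaves the Week 24 boundary unresolved: about 92% of year-only follow-up AEs would be counted as On-treatment, the sum of the two year-only shares given for Days 170–225 (61.4% + 30.9% for the earliest end date, 46.3% + 45.9% for the latest).
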